3.5.4.2 Aim 2: To test the feasibility, acceptability, and preliminary efficacy of the adapted intervention for stigma reduction, we will employ a randomized-controlled design in which we will randomize 80 Thai PLWH to two groups and follow them for 10 weeks.

3.5.4.2.1 Treatment group assignment: We propose to recruit 80 Thai PLWH who will be randomly assigned to either the Enhanced Treatment group (**ET**; $N=40$) or the Treatment-as-Usual group (**TAU**; $N=40$). While the ET group participants will receive the

proposed stigma reduction intervention, the TAU group participants will receive typical services available in the Sanpatong Hospital that are also available to the participants in the

Table 3: Sample Allocation for ET and TAU Groups (# in ET/ # in TAU)

Cisgender Straight Men	Cisgender Straight Women	MSM	Transgender	Substance User
8/8	8/8	10/10	5/5	9/9

ET group, including care co-ordination and linkage to public health nurses in local communities. Using a computer program, we will generate a list of random numbers to assign participants to either group. Numbered envelopes indicating condition assignment will be prepared and sealed. However, to ensure equivalence of gender/sexuality/substance use composition between study arms, we will stratify the sample and randomize each gender/sexuality/substance use category separately, so that each arm will consist of 40 participants with balanced gender/sexuality/substance use compositions. This balanced composition between groups will guarantee sufficient sample sizes for key subpopulations and, hence, enable subsequent analyses for possible heterogeneity of treatment effects. See **Table 3** for the sample allocation for both the ET and TAU groups. Study staff will not be aware of the assignment until the envelope is opened and the baseline survey has been performed.

3.5.4.2.2 Implementation: The stigma reduction intervention will consist of four group counseling sessions delivered by trained interventionists. In each session, a designated interventionist will meet with participants for 120 minutes in a designated room at the Sanpatong Hospital. To help build rapport among the group members, we will host, in total, 5 groups, including 1 group for cisgender straight men who are non-substance users ($n = 8$), 1 group for cisgender straight women who are non-substance users ($n = 8$), 1 group for MSM who are non-substance users ($n = 10$), 1 group for transgender individuals who are non-substance

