3.5.4.2.8.2 To evaluate preliminary efficacy: Our study design involves a two-group randomized-controlled clinical trial with four assessments for each participant and a total of 320 observations. **The study is not fully powered for efficacy, limiting the sophistication of the analyses we can conduct to test efficacy.** However, to obtain robust estimations, we will take the following steps: (a) we will examine the scope and mechanisms for missing data and attrition to investigate the extent to which the missing-at-random (MAR) assumption is violated, and, if it is violated, we will adapt procedures recommended by Barnes et al.;¹⁵¹ (b) we will examine all measures at each observation time using univariate statistics to identify potential irregular response patterns and determine overall quality of data; (c) we will assess scale reliability and compare it to published psychometrics in comparable populations; (d) we will triangulate objective and self-report measurement of adherence; (e) we will give special attention to our key primary outcome variables (quality of life and objective health measures) as well as secondary outcome variables (stigma, disclosure preparedness, family relations, family support, self-management efficacy, adherence, depressive and anxiety symptoms, and physical symptoms; note that all the outcomes are continuous); and (f) we will investigate the quality of random assignment by conducting a series of bivariate statistics comparing selected demographic, clinical, and psychosocial factors between treatment groups at baseline. Important findings may result in the modification of subsequent analyses.

[figure not shown]
We will use Generalized Estimating Equations (GEE) to test the proposed hypotheses while controlling for stratification and basic demographic backgrounds. This GEE framework allows us to carry out statistical tests for all the major hypotheses by comparing "population averages" between groups while appropriately adjusting for autocorrelations in observations due to repeated measures for the same groups of participants. We will further apply the small-sample estimator of variance to accommodate our sample size.¹⁵² To compute

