standard errors and confidence intervals for statistical inferences, we will use a clustered sandwich estimator to obtain robust estimations. Note that, for simplicity of the exposition, controlling variables are not shown in the equations. All the statistical testing will be analyzed with the statistical software packages Stata and R. **Please note, our interpretations will focus on the size of the between-group effect and its replication in the DT group because this study is not designed to have power to detect small effects.**

We will fit the following GEE intent-to-treat model with the Thai

PLWH: $g(E(Y_{it})) = \beta_{01} + \beta_{02} * Week_{i4} + \beta_{03} * Week_{i7} + \beta_{04} * Week_{i10} + \beta_{05} * I(ET_i) + \beta_{06} * I(ET_i) * Week_{i4} + \beta_{07} * I(ET_i) * Week_{i7} + \beta_{08} * I(ET_i) * Week_{i10}$ where $g(\cdot)$ denotes a proper link function; Y_{it} denotes primary or secondary outcomes in separate models for participant i at Week t ; $t = 1, 4, 7$, and 10 ; and $I(ET_i)$ denotes a binary variable indicating whether participant i belongs to the immediate treatment group. In this model, β_{01} represents the mean

outcome levels for DT at Week 1; β_{02} represents the slope for TAU between Week 1 and Week 4; β_{03} represents the slope for DT between Week 1 and Week 7; β_{04} represents the slope for TAU between Week 1 and Week 10; β_{05} represents the average group difference in outcomes between TAU and ET groups at Week 1; β_{06} represents the average group difference in the slope between TAU and ET groups between Week 1 and Week 4; β_{07} represents the average group difference in the slope between TAU and ET groups between Week 1 and Week 7; and β_{08} represents the average group difference in the slope between TAU and ET groups between Week 1 and Week 10. We define that the main between-group treatment effect is equal to β_{06} ; therefore, we expect that β_{06} will be significantly different from 0.

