3.5.4.2.8.3 Sample Size Considerations: As the goal of qualitative components is to explore a range of experiences among Thai PLWH's experiences in family relations and self-management, as well as their opinions regarding acceptability of the adapted intervention, it is critical to include participants with a wide enough range of experiences to reach conceptual saturation. Although "saturation" and "a priori determined sample size" have stimulated debates in the literature,¹⁵³⁻¹⁵⁵ it is generally agreed that a sample size of 30 participants should be sufficient to capture a range of experiences.¹⁵⁴ Therefore, the 30 in-depth interviews we utilize in our AIM 1 to revise the conceptual model, as well as the 40 exit interviews we will conduct in our AIM 2 to evaluate acceptability of the intervention, should provide sufficient saturation and guide future intervention revisions. Please note, we do not intend to fully power the quantitative data to formally test the model in this project. Rather, we will focus on the magnitude and valence of the treatment effect as well as its overall pattern during replication. However, in order to understand the size of the difference in slopes (β_{06}) between treatment groups our data can detect given our sample size, observation time points and the GEE model, we used the *liu.liang.linear.power* function in the *longpower* package¹⁵⁶ in the R statistical software and supplied with the preliminary data from our ongoing R21 project. The results are illustrated in **Figure 5**. Given our study designs with $N = 80$ and model choice (GEE), we can detect as small as 2.4 in β_{06} with 80% power.

3.5.4.3 **Aim 3: To revise and finalize the study protocols using results from AIM 1 and AIM2.**

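### Baseline comparisons between arms may reshape the efficacy analysis without limit, while the baseline adjustment that would gain power is not fixed in advance

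*Combined protocol and SAP*

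**What the plan says.** Section 3.5.4.2.8.2 lists six preparatory steps, (a) to (f), before the efficacy model. Step (f) examines how well randomization worked by "conducting a series of bivariate statistics comparing selected demographic, clinical, and psychosocial factors between treatment groups at baseline". The sentence that closes the list reads "Important findings may result in the modification of subsequent analyses". The factors to be compared, what counts as important, and which analyses may change are not stated.

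The same section uses GEE "to test the proposed hypotheses while controlling for stratification and basic demographic backgrounds". The demographic variables are not named, and the plan notes that "for simplicity of the exposition, controlling variables are not shown in the equations".

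The model has week indicators, an arm term β05 and three arm-by-week terms. On the target parameter the plan says "We define that the main between-group treatment effect is equal to" β06, the difference between arms in change from Week 1 to Week 4. Section 3.5.4.2.8.3 says of the sample of 80 that "we can detect as small as 2.4 in" β06 with 80% power. In section 3.5.4.2.1, "we will stratify the sample and randomize each gender/sexuality/substance use category separately", giving 40 per arm across five strata (Table 3).

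**The concern.** Allocation is by computer-generated list, sealed envelopes and stratification. If that is carried out properly, every baseline difference between arms is chance, so comparing the arms cannot show whether randomization worked. It can only show which chance differences this sample produced. Letting those differences alter the later analyses, with no limit, makes the final model depend on them and leaves room to choose a model after the data are seen.

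An opportunity is also missed. The covariate most likely to help is the Week 1 value of the outcome, and the printed model does not use it efficiently. Two things are at stake: the meaning of the test of β06, which the plan expects to differ significantly from zero, and the precision of an effect size that section 3.5.4.3 will use to size the next study.

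**Working it through.** **Inputs.** From the documents: 40 per arm; the model and β06 (3.5.4.2.8.2); detectable β06 of 2.4 at 80% power (3.5.4.2.8.3). Not in the text, so assumed: two-sided α = 0.05; the number of baseline factors; the Week 1 to Week 4 correlation r (range 0.4 to 0.7); equal variance σ² at both weeks; identity link (the plan calls all outcomes continuous).

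**1. The plan's own figure.** The 2.4 cannot be reproduced, because the SD, correlation and α are not in the text. Read as a change contrast, it implies an SD of change of 2.4 / [(1.960 + 0.842) × √(2/40)] = 3.83.

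**2. How often chance raises a flag.** For k independent tests at 0.05 the probability of at least one flag is 1 − 0.95^k: 40% for k = 10 and 64% for k = 20. Correlated factors would lower these figures.

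**3. Adding time-constant covariates to the printed model.** The week-by-arm structure is saturated, so with complete data β06 is the difference in mean change. A covariate that does not vary over time, entered as a main effect, cancels from it. In 150 simulated trials with the printed GEE and exchangeable correlation, the estimates with and without such a covariate differed by at most 3 × 10⁻¹⁵, and power was 68% both ways. With 15% missing after baseline, the mean SE was 1.033 without and 1.031 with the covariate.

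**4. Using the Week 1 outcome.** With n = 40 per arm:

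- Change contrast, as printed: variance = (2/n) × 2σ²(1 − r).
- Week 4 adjusted for Week 1, or Week 1 means constrained equal (β05 dropped): variance ≈ (2/n) × σ²(1 − r²).
- Ratio = (1 − r²) / [2(1 − r)] = (1 + r)/2.

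If the change contrast has 80% power, adjusted power is Φ(2.802/√[(1 + r)/2] − 1.960). The detectable effect becomes 2.4 × √[(1 + r)/2], if 2.4 belongs to the change contrast.

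| r | Variance ratio | Power, formula | Power, simulated | Adjusted only if baseline test p < 0.05, simulated | Detectable β06 |
|---|---|---|---|---|---|
| 0.4 | 0.70 | 92% | 92% | 81% | 2.01 |
| 0.5 | 0.75 | 90% | 89% | 81% | 2.08 |
| 0.6 | 0.80 | 88% | 87% | 80% | 2.15 |
| 0.7 | 0.85 | 86% | 85% | 80% | 2.21 |

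The simulated columns use 10,000 runs with 40 per arm and complete data.

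**5. Type I error.** In the same simulation, a strict rule of adjusting only after a significant baseline test is slightly conservative (4.3% to 4.8%). Reporting the better of the change and baseline-adjusted results gives about 7% to 8%. Adding a Week 4-only comparison to the choice gives about 9% to 11%.

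**6. A condition on the constraint.** Dropping β05 helps only if the working correlation is not independence. Under independence, β06 becomes the raw Week 4 difference, with variance (2/n) × σ². Its ratio to the change contrast is 1/[2(1 − r)], which is 0.83, 1.00, 1.25 and 1.67 for the four values of r. The SAP text names no working correlation.

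**The case against.** The plan already adjusts for stratification and basic demographics whatever the baseline comparisons show, and its change contrast already removes baseline differences in the outcome from β06. The closing sentence says only that findings may lead to changes. It follows the whole list (a) to (f), so it may be aimed at missing-data or data-quality findings. Efficacy is preliminary, and the plan says that it is not fully powered.

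Much of this stands. A reader might infer that the plan selects covariates by p-value. It does not say so: no test level, selection rule or adjustment is written. A reader might also infer that choosing baseline factors by test costs power in the printed model, or inflates its type I error. Step 3 shows otherwise for time-constant factors entered as main effects: with complete data and an identity link β06 does not move, and with 15% missing it hardly does. A cost arises only if the change of analysis reaches the contrast itself, for example through baseline-outcome adjustment or covariate-by-week terms.

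Two parts of the concern survive. The existing adjustment is not a fixed set to return to, because the demographics are unnamed and the equation omits them. And removing baseline differences by a change contrast is less efficient than adjusting for the Week 1 value for any r below 1.

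**Conclusion.** The point holds as an open permission, not as a faulty written rule. Step (f) and the sentence after it allow chance imbalance to alter the efficacy analysis without limit. The 40% and 64% flag rates rest on an assumed number of independent factors and an assumed level.

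The quantified benefit lies in fixing the baseline-outcome adjustment: about 5 to 12 points of power over the printed change contrast (80% to between 85% and 92%), for assumed correlations of 0.7 down to 0.4, with complete data and equal variances. Waiting for a baseline test forgoes nearly all of it. The type I error figures of 7% to 8% and 9% to 11% are worst cases that assume the most favourable result is always reported. The documents do not say that this will happen.

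Severity is modest because interpretation centres on effect size. It is not negligible, because a significance test of β06 is expected and section 3.5.4.3 carries these effect sizes into the power calculation for the next study.

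**What to change.** 1. State one primary GEE in full: either Week 1 means constrained equal across arms (β05 dropped), with a named working correlation other than independence, or Week 4 adjusted for the Week 1 outcome. Randomization justifies equal expected Week 1 means, and section 3.5.4.2.1 places the baseline survey before staff learn the assignment.
2. Include the five randomization strata and a short, named list of demographic or prognostic covariates, and show them in the equation.
3. Replace step (f) with a descriptive table of baseline characteristics by arm, without tests.
4. Reword the closing sentence so that any model prompted by baseline imbalance is a labelled sensitivity analysis. Keep the planned responses to the missing-data and data-quality checks in (a) to (d), since deleting the sentence outright would remove them.

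The cost is SAP wording only: no extra participants, visits or measurements. The detectable-effect statement in 3.5.4.2.8.3 should be recomputed for the fixed model, giving the correlation, SD and α used.

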users (n = 5), and 1 group for substance users (n = 9). The interventionist will follow the intervention manual to deliver the intervention and assign homework for group members to practice on their own. In the following sessions, the interventionist will review progress with participants, guide participants through exercises, and identify additional problems to be addressed in subsequent sessions.

3.5.4.2.3 Fidelity check: To ensure intervention fidelity, all the intervention sessions will be audio-recorded and interventionists' progress notes will be reviewed for supervision purposes; in addition, subsequent analysis of interventionists' reliability will be conducted. At the end of each month, the Thai-speaking researchers and the team will randomly select and review 20% of the recordings and progress notes throughout the study period. The research staff will host biweekly supervision sessions for the interventionists to discuss difficult cases, including their intervention decisions. Finally, the PIs ([name] and [name]) will travel to the study site at least twice a year to provide oversight to the research personnel. The PIs will also be available daily through online communication with the research personnel for immediate troubleshooting to ensure smooth research operations. Drs. [name], [name], and [name] will meet regularly and frequently online to review progress, solve emerging issues during project operations, and revise the plans for action.

3.5.4.2.4 To minimize attrition, we will implement specific procedures beginning at baseline. The procedures, which we successfully employed in prior projects, include verifying contact information at each assessment, obtaining any potential upcoming changes in addresses every month, using potential friend and family locators, collecting email addresses, and sending cards when approaching follow-up dates. Based on our prior experiences, we expect that attrition will be lower than 15% with application of these procedures. Therefore, we aim to recruit $80/(1-0.15) = 94$ participants at our baseline, which after attrition may result in a sample of 80 for analysis.

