3.5.4.2.7 A summary flowchart of the randomized waitlist-controlled trial

A flowchart is presented in **Figure 4** to summarize recruitment, enrollment, randomization, intervention delivery, and assessments. Please note that, for the ET group, the Week 1 assessment occurs right before the first intervention session, and the Week 4 assessment occurs right after the fourth intervention. In contrast, for the TAU group, there is no additional stigma reduction intervention, but the group will be assessed at Weeks 1, 4, 7, and 10. The same 3-week intervals will enable direct comparisons across conditions and assessments.

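### With one ET therapy group per stratum, the β06 interval and the 2.4 make no stated allowance for therapy-group correlation, which matters for inference beyond these five groups, and a stratum difference cannot be attributed to the subpopulation

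*Combined protocol and SAP*

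**What the plan says.** - **Delivery (3.5.4.2.2).** ET is counselling in groups, over four sessions of 120 minutes: "we will host, in total, 5 groups". The groups are defined by the same five categories that serve as randomization strata in 3.5.4.2.1 and Table 3, with 8, 8, 10, 5 and 9 ET participants. Each stratum therefore has exactly one ET therapy group.
- **Comparator (3.5.4.2.7).** "for the TAU group, there is no additional stigma reduction intervention", so TAU has no study therapy groups.
- **Model (3.5.4.2.8.2).** The GEE is indexed by participant and week and has no therapy-group term. It is described as "appropriately adjusting for autocorrelations in observations due to repeated measures for the same groups of participants", and hypotheses are tested "while controlling for stratification and basic demographic backgrounds". For standard errors, "we will use a clustered sandwich estimator to obtain robust estimations"; the cluster unit is not named. The main effect is β06, the arm difference in change from Week 1 to Week 4, and the plan expects that it "will be significantly different from 0".
- **Detectable difference (3.5.4.2.8.3).** With N = 80 and 80% power the plan gives 2.4 for β06. The listed basis is the sample size, the time points, the GEE model and data from the R21 project.
- **Subgroups (3.5.4.2.1).** The balanced allocation "will guarantee sufficient sample sizes for key subpopulations and, hence, enable subsequent analyses for possible heterogeneity of treatment effects".

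**The concern.** People who share a therapy group share its sessions, its interventionist and each other's company. Section 3.5.4.2.2 forms the groups partly so that members build rapport. Their changes after Week 1 may therefore be more alike than those of unrelated participants, in ET only. A sandwich variance clustered on participant does not see this correlation.

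Two things are at stake:

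- **Precision.** The interval and test for β06 would be too optimistic for anyone who takes the result to new therapy groups. That use is foreseen: 3.5.4.3 bases the sample size of the future R01 on effect sizes from this trial.
- **Attribution.** If one stratum appears to benefit and another does not, the reason may be the subpopulation or may be the one therapy group in which that stratum was treated.

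**Working it through.** **The plan's own figure.** The 2.4 cannot be reproduced, because the text gives no SD, within-person correlation, alpha or sidedness. With the two-means normal formula and an assumed two-sided 0.05, 2.4 = (1.960 + 0.842) × SD × √(2/40), which implies an SD of change of 3.83. The steps below only rescale 2.4 and do not need this SD.

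**Inputs.** ET group sizes 8, 8, 10, 5, 9 (3.5.4.2.2); 40 per arm (3.5.4.2.1); 2.4 at 80% power (3.5.4.2.8.3). The ICC is the correlation of Week 1 to Week 4 changes within an ET group. It is not in the documents; 0.02, 0.05 and 0.10 are assumed.

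**Formulas.**

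1. Effective group size = Σm²/Σm = (64 + 64 + 100 + 25 + 81)/40 = 334/40 = 8.35.
2. ET design effect = 1 + (8.35 − 1) × ICC = 1 + 7.35 × ICC.
3. Only ET is grouped and the arms are equal in size, so the variance ratio for β06 = (ET design effect + 1)/2.
4. SE multiplier f = √(variance ratio).
5. Detectable difference = 2.4 × f; power at 2.4 = Φ(2.80/f − 1.96).

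| ICC | ET design effect | Variance ratio | f | Detectable difference | Power at 2.4 |
|---|---|---|---|---|---|
| 0 | 1.000 | 1.000 | 1.000 | 2.40 | 80% |
| 0.02 | 1.147 | 1.074 | 1.036 | 2.49 | 77% |
| 0.05 | 1.368 | 1.184 | 1.088 | 2.61 | 73% |
| 0.10 | 1.735 | 1.368 | 1.169 | 2.81 | 67% |

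**Type I error of the participant-level test, by simulation (no true effect, t with 78 df).**

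| Setting | Runs | ICC 0 | 0.02 | 0.05 | 0.10 |
|---|---|---|---|---|---|
| Change scores | 100,000 | 5.0% | 5.7% | 7.1% | 9.4% |
| Four-visit GEE, stratum main effects, small-sample sandwich on participant (within-person correlation 0.6 assumed) | 20,000 | 4.4% | 5.4% | 6.9% | 9.8% |
| Change scores, group effects centred to average zero over the five groups | 100,000 | – | 4.9% | 4.8% | 4.5% |

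The first two rows treat the five groups as a sample of possible groups; the third takes the average over these five as the target. Mean β06 in the GEE simulation stayed at about 0, so the estimate is not biased. Multiplying the ET variance by 1 + 7.35 × ICC brought the error back to 4.9–5.2% (change scores) and 4.7–4.9% (GEE).

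**Does stratum adjustment deal with it?** No. A stratum main effect is common to both arms and all visits, whereas a shared-group effect arises only in ET and only after baseline. The GEE simulation included stratum terms and was still inflated.

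**Is stratum membership itself the problem?** No. With a stratum trend common to both arms (2%, 5% or 10% of change variance) and no shared-group effect, type I error was 4.9%, 4.5% and 4.0%.

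**Attribution.** Within ET, the five therapy-group indicators and the five stratum indicators are the same columns. ET-by-stratum and therapy-group effects are fully aliased at any ICC and any sample size.

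**The case against.** The strongest reply concerns the target of inference. The five groups are also the five strata, fixed by design. If the target is the average effect over these five as run, the participant-level interval is adequate, as the centred simulation shows. This stands. A reader might infer that the planned interval is simply wrong; the documents do not support that, and the point is limited to inference beyond these groups.

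The size is also wholly assumed. At an ICC of 0 nothing is wrong, and at 0.02 the 2.4 becomes only about 2.5. Manualised delivery, review of 20% of recordings and biweekly supervision (3.5.4.2.3) may reduce differences due to interventionists, though they do not bear on peer effects. Participant-level clustering is inferred, since the cluster unit is unnamed. It is the likely reading, because repeated measurement is the only source of correlation described. Clustering on therapy group would not help: five ET clusters are too few for a reliable sandwich variance.

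The plan says that it is not fully powered for efficacy and will focus on effect size. That lowers the stakes, but a warning about low power is not a warning about an interval that is too narrow.

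Finally, a reader might infer from the aliasing that the subgroup sample sizes are insufficient. It does not show that. The effect of ET as delivered can still be estimated in each stratum; what is lost is the ability to say why strata differ.

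**Conclusion.** The concern holds in a limited form. If changes are correlated within ET therapy groups, the participant-level interval and test for β06 are too optimistic for inference beyond these five groups. At assumed ICCs of 0.02, 0.05 and 0.10 the SE for that wider inference is about 4%, 9% and 17% larger, type I error is about 5.5–6%, 7% and 9–10%, and the detectable difference is about 2.5, 2.6 and 2.8. These figures assume two-sided 0.05, equal variance of change in the two arms, and the planned group sizes. The point estimate is unaffected.

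The attribution point needs no assumed ICC: a treatment-by-stratum difference is a difference between stratum and therapy group combined. The heterogeneity analyses foreseen in 3.5.4.2.1 can be run, but they cannot assign a difference to the subpopulation. This is a cheap improvement to the plan; it does not invalidate the design.

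**What to change.** 1. **3.5.4.2.8.2.** State that the sandwich estimator clusters on participant and that the primary interval does not cover variation between therapy groups. Add a sensitivity table for β06 at ICC 0.02, 0.05 and 0.10, with the ET part of the variance multiplied by 1 + 7.35 × ICC (the factor recomputed from the analysed group sizes). Keep the participant-level degrees of freedom, about 78, because the ICC is assumed and not estimated. Label the table as inference beyond these five groups.
2. **3.5.4.2.8.3.** State that 2.4 assumes no therapy-group correlation, and give about 2.5, 2.6 and 2.8 at those ICCs. If the R21 inputs did allow for it, say so instead.
3. **3.5.4.2.1.** State that subgroup estimates are descriptive, are shown with 95% confidence intervals, and reflect stratum and therapy group combined.

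The cost is a few sentences and one table, with no change to design or conduct. The downside is wider sensitivity intervals and a slightly less favourable detectable difference.

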The study protocols have two parts, including intervention protocol and operational protocol. The intervention protocol is the intervention manual providing a detailed, step-by-step guide for each of the intervention sessions. The goals, topics, intervention approaches, and timeframe for each module will be clearly delineated. We will use the study results from AIM 2—the feasibility, acceptability, and effect sizes—to finalize the intervention protocol. Since our intervention will be adapted using the qualitative data from our prior studies with additional input from stakeholders, we expect most intervention components will be feasible and acceptable to our participants; yet, by using the qualitative data from exit interviews and study logs, we will identify specific intervention components in need of revision, and particularly those clearly not acceptable to Thai PLWH. To further increase feasibility and acceptability of the intervention, we will recommend additional

adjustments to the intervention and submit them to the CAB and SAB for final review. We will calculate power and required sample size of the future R01 study using the preliminary effect sizes from the current project.

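### The main effect β06 is a raw change-from-baseline contrast; adjusting the Week 4 comparison for the Week 1 score would estimate the same effect more precisely at no extra data cost

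*Combined protocol and SAP*

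**What the plan says.** Section 3.5.4.2.8.2 specifies a GEE with an intercept, indicators for Weeks 4, 7 and 10, an ET indicator and three ET-by-week terms. Week 1 is one of the four outcome times. The ET coefficient β05 "represents the average group difference in outcomes between TAU and ET groups at Week 1", and nothing fixes it at zero. For the main effect the section states "We define that the main between-group treatment effect is equal to" β06, the ET–TAU difference in change from Week 1 to Week 4.

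The model is fitted "controlling for stratification and basic demographic backgrounds"; these terms are left out of the displayed equation. No section names the Week 1 value of the outcome as a covariate. Step (e) adds "note that all the outcomes are continuous". Step (f) compares the arms at baseline and then says "Important findings may result in the modification of subsequent analyses".

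On purpose, the section says "The study is not fully powered for efficacy" and that "our interpretations will focus on the size of the between-group effect". Section 3.5.4.3 (Aim 3) then says "We will calculate power and required sample size of the future R01 study using the preliminary effect sizes from the current project".

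**The concern.** With a free β05 and the Week 1 score as an outcome, β06 subtracts the whole baseline difference between arms from the Week 4 difference. Randomisation makes the expected baseline difference zero, so this subtraction removes no bias. It does add noise unless the Week 1 and Week 4 scores are almost perfectly correlated. Regression on the Week 1 score removes only the share of the baseline difference that predicts Week 4.

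What is at stake is precision in a trial of 80 people whose main quantitative product is an effect size that will set the sample size of the next study. Feasibility and acceptability (Section 3.5.4.2.8.1) are unaffected, and no decision rule in the documents changes.

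**Working it through.** **Inputs from the documents.** 40 per arm; strata as in Table 3; ET delivered in five groups of 8, 8, 10, 5 and 9 (Section 3.5.4.2.2); continuous outcomes, so an identity link; time-constant controls.

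**Assumed.** ρ, the Week 1–Week 4 correlation, from 0.3 to 0.9; equal SDs σ at the two visits; a shared ET group variance τ² of 0, 0.05σ² or 0.10σ².

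**The plan's own figure.** Section 3.5.4.2.8.3 gives a detectable β06 of 2.4 at 80% power with N = 80. It cannot be reproduced, because the SD, correlation and alpha are not in the text. Back-solving at an assumed two-sided 0.05 gives SE = 2.4/(1.960 + 0.842) = 0.857, and so an SD of change of 0.857/√(2/40) = 3.83.

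**Step 1: β06 is the raw change contrast.** The arm-by-week means are saturated and the controls do not vary over time, so they cancel from β06. On one simulated complete data set, with stratum and age in the model, β06 was 0.040657 under both independence and exchangeable working correlation. The difference in mean change was also 0.040657. On a second data set, adding the Week 1 score as a further main effect while Week 1 stayed an outcome row still left β06 at the raw change difference (−1.3126). Extending the control list therefore does not help.

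**Step 2: variances, n per arm.**
- Change contrast: 4σ²(1−ρ)/n
- Week 4 adjusted for Week 1: 2σ²(1−ρ²)/n
- Ratio: 2(1−ρ²)/[4(1−ρ)] = (1+ρ)/2

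With unequal SDs s1 and s4, the change contrast exceeds the adjusted one by an amount proportional to (s1 − ρ·s4)². This is never negative, so the direction does not depend on equal SDs.

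**Step 3: shared ET group effect.** This adds τ²·Σm²/n² to both variances. Here Σm² = 64 + 64 + 100 + 25 + 81 = 334, and 334/1600 = 0.209. Adjustment cannot remove this term, so it pulls the ratio towards 1.

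**Step 4: simulation.** Table 3 strata, estimated slope, 40,000 trials per case. Entries are adjusted variance divided by change variance, with the fall in standard error in brackets.

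| ρ | (1+ρ)/2 | τ² = 0 | τ² = 0.05σ² | τ² = 0.10σ² |
|---|---|---|---|---|
| 0.3 | 0.65 | 0.666 (18%) | 0.708 (16%) | 0.735 (14%) |
| 0.5 | 0.75 | 0.757 (13%) | 0.803 (10%) | 0.830 (9%) |
| 0.7 | 0.85 | 0.862 (7%) | 0.902 (5%) | 0.920 (4%) |
| 0.8 | 0.90 | 0.919 (4%) | 0.943 (3%) | 0.958 (2%) |
| 0.9 | 0.95 | 0.964 (2%) | 0.981 (1%) | 0.991 (under 1%) |

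The adjusted estimate was not less precise in any of the 15 cases.

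**Step 5: the proposed model itself.** Weeks 4, 7 and 10 as outcomes, baseline by week, stratum, exchangeable correlation, 8,000 trials, no group effect. The Week 4 variance ratios were 0.652, 0.748, 0.864, 0.919 and 0.958 in the same order of ρ. Mean estimates under a null effect were within 0.003 SD of zero.

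**Step 6: scale of the plan's 2.4.** If 2.4 refers to the change contrast, the adjusted analysis detects 2.4·√((1+ρ)/2) = 1.93, 2.08, 2.21, 2.28 and 2.34 in the same order of ρ. This is an illustration only, since the power inputs are not shown.

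**The case against.** The strongest reply is that this is a preference about efficiency in a pilot that disclaims power, and that the gain may be slight. Assessments three weeks apart on a scale with α above 0.90 (Table 4) are compatible with a high ρ. At ρ of 0.8 or more the standard error falls by 4% at most, and above about ρ = 0.97 the cost of estimating the slope cancels the gain. That stands as a limit on size. It does not favour the change contrast at any ρ examined, and limited power is a reason to use the baseline score.

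Other points, and what remains of them:

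- **Missing data.** Section 3.5.4.2.4 allows for up to 15% attrition, and exact equality with raw change needs complete data. Suppose 15% of each arm is lost at random before Week 4 and the exchangeable correlation is correct. The ratio is then (1+ρ)/[(1+ρ) + 0.85(1−ρ)] = 0.69, 0.78, 0.87, 0.91 and 0.96 for ρ = 0.3, 0.5, 0.7, 0.8 and 0.9. The gain shrinks slightly and survives.
- **Week 1-only participants.** The covariate model drops anyone with no later visit, whereas the plan's model keeps that record. This is correct; the constrained alternative given with the fix keeps them.
- **Scope.** The section allows other link functions, and clinic visits are counts of missed or delayed visits (Table 4). The algebra is secure for the internal stigma sum score, but not automatically for every outcome.
- **Knock-on text.** The 2.4, the count of 320 observations and the TAU change parameters β02 to β04 all belong to the current model. This stands as an editing task. Over the range of ρ considered, 2.4 becomes at most slightly conservative.
- **Coverage.** Interval coverage with the planned small-sample sandwich variance was not examined, and the proposed model was simulated without group effects.

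Step (f) does not answer the concern. It permits an unspecified change after looking at baseline balance, whereas the adjustment should be fixed in advance.

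**Conclusion.** The concern holds. The planned main effect is unbiased, but it discards precision that the Week 1 score would supply for the same Week 4 target. The direction is firm for continuous outcomes with an identity link and ρ up to 0.9. The size depends on ρ, which the documents do not give: roughly 9% to 18% off the standard error at ρ of 0.3 to 0.5 across the group variances considered, and 4% or less at 0.8 and above. The change is worth making because the effect estimate is the stated focus and feeds the next trial's sample size. It is a recommended improvement, not the correction of an invalid analysis.

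**What to change.** In Section 3.5.4.2.8.2, take Weeks 4, 7 and 10 as the outcomes. Include the Week 1 value of the same outcome as a covariate interacting with week, plus the randomisation stratum and the demographic controls. Keep the ET–TAU contrast at Week 4 as the main effect. State that this adjustment applies whatever the step (f) comparisons show.

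If Week 1 is kept as an outcome with β05 set to zero, so that participants with only a Week 1 record still contribute, specify an unstructured working correlation. Under independence that version is the unadjusted Week 4 difference, with variance 1/(2(1−ρ)) times that of the change score. In simulation this was 0.72, 1.00, 1.67, 2.52 and 5.00 times at ρ = 0.3, 0.5, 0.7, 0.8 and 0.9.

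Two consequential edits follow. Say in Section 3.5.4.2.8.3 that 2.4 was computed for the change contrast, or recompute it from the R21 data. Reword the parameter definitions and the observation count. It would also help to state that participants complete the Week 1 survey before learning their assignment. Section 3.5.4.2.1 says this of study staff, and the sealed envelopes largely imply it.

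The cost is one model line, the related SAP wording and about one degree of freedom per visit (nine core mean parameters in place of eight). No new data or participants are needed.
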